### **1.1.2 Footnotes**

Footnotes on outputs will be kept to a minimum also for outputs not covered in [\[Efficacy MAP M7.1\]](#) or [\[Safety MAP M7.1\]](#).

Footnotes will generally be provided for

- abbreviations used in the output; abbreviations used on several outputs, e.g. for listings in [Appendix 16.2](#) can be presented on a separate page and do not have to be repeated as footnotes on each listing
- sorting order of categories, e.g. for sorting within MedDRA (Medical Dictionary for Regulatory Activities) hierarchy levels
- MedDRA version used for reporting of MedDRA coded data

Footnotes will generally NOT be given for

- units displayed on the output
- interpretation of results (e.g. “odds ratio larger 1 favors active treatment”)
- information that can be retrieved from the statistical section of the clinical study report (CSR) unless it is not identifiable from the output, e.g.
  - explanation of analysis model used unless results of more than one model are displayed on an output
  - derivations of variables (e.g. BMI will not be explained on a footnote)
- information that will be provided in the clinical study protocol and/or methods section of the CSR (e.g. baseline definition if this is specified in the statistical section of the CSR)

## 1.2 Subjects and treatments

The following analysis sets will be used for the data analysis.

**Extension Full analysis set (FAS):** The FAS will be comprised of all subjects from the randomized set to whom study treatments has been assigned and entered the extension study. Following the intent-to-treat principle, subjects will be analyzed according to the treatment assigned to at randomization in A2304 and A2307 and thereafter reassigned to treatment at Week 156. If the actual stratum is different to the assigned stratum in IRT, the actual stratum will be used in analyses.

Of note, subjects excluded from the randomized set will be excluded from the FAS.

**Extension Safety set:** The safety set includes all subjects who took at least one dose of study treatment during the extension treatment period. Subjects will be analyzed according to treatment received. The treatment received will be set to the treatment randomized. But if a subject has received the wrong treatment during the entire study, the treatment received will be set to this wrong treatment.

**Table 1-1 Subject classification rules**

| Analysis set            | PD Population Codes that cause subject to be excluded | Non-PD criteria that cause a subject to be excluded |
|-------------------------|---|---|
| FAS (Full Analysis Set) | GCP01, GCP06, INCL01, INCL16, INCL18                  | No post baseline efficacy assessment                |
| Safety                  | GCP01, GCP06, INCL01, INCL16, INCL18                  | Not treated in the extension                        |

Note: Protocol Deviation (PD) Populations Codes are available from the study DHP (Data Handling Plan).

**Core study A2304:** Randomization was stratified by geographical region and by body weight collected at Visit 2 (< 90 kg or  $\geq$ 90 kg). In study sites selected for psoriatic arthritis assessments according to ACR criteria, randomization was also stratified according to history of psoriatic arthritis at screening.

Subjects were randomized using a 1:1 ratio into one of the treatment groups below:

- **Secukinumab 150 mg group:** AIN457 150 mg s.c. q week x 5 followed by 150 mg s.c. q 4 weeks
- **Secukinumab 300 mg group:** AIN457 300 mg s.c. q week x 5 followed by 300 mg s.c. q 4 weeks

At Week 12 in core study A2304, subjects were classified into 3 categories:

**PASI non-responders:** were discontinued from study

**PASI partial responders:** were offered participation into trial CAIN457A2307.

**PASI 75 responders:** within each dose group (150 or 300 mg s.c.) were re-randomized to one of the two maintenance treatment arms in a ratio of 1:1 (either “fixed interval” or “retreatment at start of relapse”) from Week 12 to Week 48.

Thus re-randomization will result to four treatment arms overall in A2304 and also one treatment arm in A2307:

**Fixed-time interval regimen – “FI” either 150 or 300 mg s.c. secukinumab:** In the maintenance period subjects will receive the same dose they received during the induction period. Thus, secukinumab 150 mg subjects will continue to receive 150 mg secukinumab every four weeks, and secukinumab 300 mg subjects will continue to receive 300 mg secukinumab every four weeks, from week 12 up to and including week 48.

**Retreatment at start of relapse regimen – “SOR”: “start of relapse” either 150 or 300 mg s.c. secukinumab:** “Start of relapse” will be defined as a loss of  $\geq 20\%$  of the maximum PASI gain achieved during the study compared to baseline, *and* a loss of PASI 75 response. Whenever a subject fulfills the start of relapse criteria, active secukinumab will be administered at their scheduled visits (i.e. every four weeks) until the subject is back to PASI 75 response. The dose administered in the maintenance period (secukinumab 150 mg or 300 mg) will be identical to the dose that these subjects received during the induction period. If a subject does not fulfill the criteria of a start of relapse or is back to PASI 75 response after a start of relapse, they will receive placebo injections (two injections per dose) to maintain the blind. This treatment regimen is applied every four weeks, from week 12 up to and including week 48.

**Open label (OL) 300 mg s.c. secukinumab:** All the partial responders at week 12 in induction period in A2304 will enter A2307 double blind i.v. period (for 8 weeks) and these subjects will be randomized with 1:1 ratio into either “300 mg s.c. secukinumab” or “10 mg per kg i.v. secukinumab”. All the subjects will enter open label 300 mg s.c. secukinumab maintenance period from week 8 to week 40.

All the subjects who are eligible from the above 5 treatment groups (4 treatment groups from A2304 and 1 treatment group from A2307) enter the A2304E1 extension study treatment period and continue with same treatment groups. At Week 156, patients under AIN457 150mg FI arm, AIN457 150mg SOR arm, and AIN457 300mg SOR arm could be switched to AIN457 300mg FI arm as determined by physician’s judgement.

For the final analysis, data will be presented for the following treatment groups:

- AIN457 150 mg FI
- AIN457 150 mg FI switch to AIN457 300mg FI
- AIN457 150 mg FI combined non-switch and switch
- AIN457 300 mg FI
- AIN457 150 mg SoR non-switched
- AIN457 150mg SoR switch to AIN457 300mg FI
- AIN457 300 mg SoR non-switched
- AIN457 300mg SoR switch to AIN457 300mg FI
- AIN457 300 mg OL
- Any AIN457 300mg
- Any AIN457 150mg
- Any AIN457

Note: any AIN457 300mg (including AIN457 150mg FI switch to AIN457 300mg FI, AIN457 300mg FI, AIN457 150mg SoR switch to AIN457 300mg FI, AIN457 300mg SoR, AIN457 300mg SoR switch to AIN457 300mg FI and AIN457 300mg OL); any AIN 150mg (including AIN457 150mg FI and AIN457 150mg SoR); Any AIN457 including all the groups above.

The following study periods will be considered for analysis:

- **Extension study period:** Week 52 post-dose to Week 268;
- **Entire study period:** Combination of Induction (in A2304 core) period + Maintenance (in A2304 and in A2307) period + Core follow-up period (consider only for subjects who enter E1 after core follow-up period) + Treatment period in E1 [Initial Randomization in A2304 core to week 268] (including follow-up period);
- **Entire treatment period:** Combination of Induction (in A2304 core) period + Maintenance (in A2304 and in A2307) period + Core follow-up period (consider only for subjects who enter E1 after core follow-up period) + Treatment period in E1 [Initial Randomization in A2304 core to week 260]
- **Follow-up 2 period:** after W268 visit to end of the study.

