**Table 1-2 Analysis by treatment group**

| Endpoint/analysis  | AIN457 150 mg FI
AIN457 150 mg FI switch to 300mg FI
AIN457 300 mg FI
AIN457 150 mg SoR
AIN457 150 mg SoR switch 300 mg FI
AIN457 300 mg SoR
AIN457 300 mg SoR switch 300 mg FI
AIN457 300mg OL | AIN457 150mg FI(NSW+SW) | Any AIN457 150mg
Any AIN457 300mg | Any AIN457 |
|--|--|-------------------------|--------------------------------------|------------|
| Subject disposition  | X  |                         |                                      | X          |
| Demography & baseline characteristics                        | X  |                         |                                      | X          |
| Previous & concomitant medication                            | X  |                         |                                      | X          |
| Medical history  | X  |                         |                                      | X          |
| Study medication: duration of exposure                       | X  |                         | X                                    | X          |
| Maintanance of PASI 75 response                              | X  |                         |                                      |            |
| PASI 50/75/90/100 and IGA mod 2011 0 or 1 response over time | X  | X                       |                                      |            |
| PASI score over time   | X  | X                       |                                      |            |
| IGA mod 2011 score over time                                 | X  | X                       |                                      |            |
| Relapse  | X  |                         |                                      |            |
| Rebound  | X  |                         |                                      |            |
| DLQI 0 or 1 achievement                                      | X  | X                       |                                      |            |

|                          |  |                         |                                      |            |
|--------------------------|--|-------------------------|--------------------------------------|------------|

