### **1.6 Study medication**

The analysis of study treatment data will be based on the safety set.

The number of planned and actual injection number will be summarized by yearly interval (analysis visit) for entire treatment period and treatment group AIN457 150 mg FI and AIN457 300 mg FI.

In case it cannot be identified from the data collected or assumed from the planned treatment whether an injection contained placebo or secukinumab, it will be assumed that the syringe contained secukinumab. For example this applies to the 150 mg secukinumab treatment group (in which subjects should receive both an active and a placebo injection) if only one injection is given. If the medication pack number is not available, it will be assumed that the secukinumab injection was applied. If this scenario occurs for subjects in the 300 mg treatment group when subjects should receive two identical injections, it will be assumed that they received secukinumab as planned.

The duration of exposure to study drug will be summarized by treatment group and yearly interval for entire treatment period.

Duration of exposure will be defined and summarized as follows:

For extension study period, duration of exposure will be defined as the time from first dose of study medication in extension 1 to the end of treatment period in extension 1 study; and for entire study period duration of exposure will be defined as the time from first dose of study medication in core study to the end of treatment period in extension 1 study. The end of treatment period will be defined as the last dose plus 84 days or last visit whichever occurs earlier. i.e., for subjects who discontinued or have their last visit earlier than last dose plus 84 days, the end of study treatment exposure will be the date of the last study visit in the corresponding treatment period.

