**Duration of exposure (days)=min(End of study visit date, last dose date + 84 days) - first dose date + 1**

Duration of exposure (years) = duration of exposure (days) / 365.25

Duration of exposure (100-patient years) = duration of exposure (years) / 100

The analyses of duration of exposure described above will be done for the extension study period and for the entire study period.

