## **1.9 Standard safety evaluation**

All safety analyses will be based on the safety set. Core study baseline will be used for all change from baseline analysis.

Absolute and relative frequencies and exposure time adjusted incidence rate or event rate analysis will consider all the events (AEs/SAEs and clinically significant newly occurring lab, vitals and ECG abnormalities) that occurred in core studies and extension study for entire treatment period and in extension study for treatment period in E1.

Safety analyses will be performed on treatment received or actual treatment (See [Section 1.2](#)).

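### The pooled safety columns report 150-to-300 mg switchers' events and time before Week 156 as 300 mg, because no SAP rule splits them at the switch

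*SAP*

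**What the plan says.** SAP Section 1.2 provides that at Week 156 subjects in either 150 mg arm, or in the 300 mg SoR arm, "could be switched to AIN457 300mg FI arm as determined by" the physician. The list of final-analysis groups then separates switched from non-switched subjects and adds one group combining both for 150 mg FI.

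The note under that list defines the pools. One is "any AIN457 300mg (including AIN457 150mg FI switch to AIN457 300mg FI, AIN457 300mg FI", continuing to the 150 mg SoR switchers, the other 300 mg groups and the open-label group. The other is "any AIN 150mg (including AIN457 150mg FI and AIN457 150mg SoR", with no switch group. Table 1-2 marks both pooled dose columns for "Study medication: duration of exposure" and for the safety analysis.

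- **Exposure (SAP 1.6).** For the entire study period it is "the time from first dose of study medication in core study to the end of treatment period in extension 1 study", computed as "Duration of exposure (days)=min(End of study visit date, last dose date + 84 days) - first dose date + 1".
- **Events (SAP 1.9).** The summaries count those "that occurred in core studies and extension study for entire treatment period".
- **Attribution (SAP 1.2, Safety set).** "The treatment received will be set to the treatment randomized", except where the wrong treatment was given throughout the study. The FAS definition mentions reassignment at Week 156; the Safety set definition does not. SAP 1.9 says safety follows treatment received or actual treatment, and refers back to Section 1.2.
- **Switch date.** It appears once among the safety rules, in the AE exposure-time derivation of SAP 1.9.1, as a possible censoring day for subjects without an event. It is absent from SAP 1.6, the laboratory censoring rule in 1.9.1, the crude incidence in 2.3.1 and the general rate in 2.4.1.

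**The concern.** Long-term safety is the primary objective, and the two pooled dose columns are where a reader looks for safety by dose. A switcher spent the core study and the first two extension years on a 150 mg regimen; for SoR subjects that includes placebo visits (Protocol 5.2). If the whole record sits in Any 300 mg, earlier events and time carry the wrong dose label, and Any 150 mg loses them.

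For most adverse events this is mixing. For events that end participation, such as death or an AE leading to discontinuation, it has a direction. A subject can switch only by reaching Week 156 alive and on treatment, so a switcher's earlier time contains no such event by construction. Removing that time from Any 150 mg raises its rate.

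**Working it through.** **1. The plan's own planning figures (Protocol 9.7), used for group size.** 918 × 0.95 × 0.85 = 741.3 (stated: about 740). 741.3 × 0.80 / 4 = 148.3 (stated: about 148). 1 − 0.999^148 = 13.8% and 1 − 0.99^148 = 77.4% (stated: 14% and 77%). All reproduce. 740 − 4 × 148 = 148 remain for the open-label group, which supports five equal groups as a working assumption.

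**2. One completing switcher.** Pre-switch share to Week 260: 156/260 = 60%. By the SAP 1.6 formula on the Table 1-8 days, exposure runs from Day 1 to min(1877, 1793 + 84) = 1877 days. Of these, 1092 (58%) precede Day 1093 (Week 156). For the extension to Week 268: 104/216 = 48%.

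**3. Share of Any 300 mg person-time to Week 260.** Let s be the share of 150 mg subjects who switch. Assume five equal groups and no drop-out. Three groups are always 300 mg and 2s groups' worth of switchers join them.

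Share = 2s × 156 / [260 × (3 + 2s)]

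For s = 10%, 25%, 50%, 75% this gives 3.75%, 8.6%, 15.0%, 20.0%. The time missing from Any 150 mg, 2s × 156 / [2s × 156 + 2(1 − s) × 260], is 6.3%, 16.7%, 37.5%, 64.3% of all 150 mg-regimen time.

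**4. Does the SAP 1.9.1 switch date repair this?** Take an event-free switcher at Day 1093. Over the whole period the rule credits Day 1 to Day 1093 and nothing later: the 150 mg time is kept and the 300 mg time is dropped. By year:

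- Year 3: 1093 − 731 + 1 = 363 days
- Year 4: 1093 − 1096 + 1 = −2 days
- Year 5: 1093 − 1461 + 1 = −367 days

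A switcher with an event in Year 4 or 5 still counts, because the ending day for subjects with events has no switch term. The rule does not work after the switch.

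**5. Direction for events that end participation (illustration).** Assume a true rate of 2 per 100 patient-years on both doses, Weeks 52 to 260, and a share s of 150 mg subjects event-free at Week 156 switching. With group size 1 and s = 25%, 104 weeks = 1.993 years and survival to Week 156 is exp(−0.02 × 1.993) = 0.961, so switchers number 2 × 0.25 × 0.961 = 0.480.

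- Any 300 mg events: 3 × 0.0766 + 0.480 × 0.0391 = 0.2487. Time under SAP 2.4.1: 13.391 years. Rate 1.86.
- Any 150 mg events: 0.1345. Time: 5.767 years. Rate 2.33.
- Ratio 1.857/2.332 = 0.80.
- Under SAP 1.9.1, event-free switchers lose their post-switch time, 0.480 × 1.993 × 0.961 = 0.920 years. Any 300 mg time is 12.471, the rate 1.99 and the ratio 0.86.

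| Switching | 300 v 150 rate, SAP 2.4.1 | Ratio, SAP 2.4.1 | Ratio, SAP 1.9.1 |
|---|---|---|---|
| 10% | 1.94 v 2.11 | 0.92 | 0.95 |
| 25% | 1.86 v 2.33 | 0.80 | 0.86 |
| 50% | 1.75 v 2.99 | 0.58 | 0.67 |
| 75% | 1.67 v 4.91 | 0.34 | 0.40 |

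The correct ratio is 1.0, and splitting at the switch returns 2.0 in both columns.

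**The case against.** No sentence in the SAP says that pre-switch data count as 300 mg. The reference to actual treatment in SAP 1.9 and the switch date in 1.9.1 suggest that a split may have been meant. The programming specifications (PDS) and RAP M8, which the SAP cites for detail, are not available here. The pools can also be read by phase: the 150 mg groups hold data up to the switch and the switch groups hold data after it. On that reading the note is right. But the group list names SoR subjects as non-switched and has a group combining switched and non-switched subjects. Those are groups of people, not phases, and no rule gives a post-switch start day. The actual-treatment wording leads back to Section 1.2, which contains no split.

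The Safety set sentence should not be pressed into a flat contradiction. Its exception concerns a wrong treatment given throughout, and a planned switch may lie outside what it was written for. It points the other way from the pooling note, and the SAP does not say which governs.

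Much is already shown. Table 1-2 gives every switch and non-switch group its own column. The yearly AE tables nearly separate the phases, since Year 3 ends on Day 1095, two days after Week 156. They cover only the FI cohorts, however, and neither feature corrects the pooled columns.

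A reader might infer from the table above that the report will show far fewer deaths or discontinuations on 300 mg. The documents do not support that. SAP 1.9.1 names no exposure-adjusted rates for those events, only separate summaries. The switch share is unknown. Under the SAP 1.9.1 rule the Any 300 mg rate stays between 1.98 and 2.00, so the distortion is almost all in Any 150 mg.

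**Conclusion.** The point holds on the text. As written, the pooled dose columns assign switchers' whole records to 300 mg, and no rule in the SAP cuts them at the switch. The firm figure is 60% of each completing switcher's time to Week 260. The 3.8% to 20% of Any 300 mg person-time rests on assumed equal groups, no drop-out and an assumed switch share. No drop-out is a simplification: about 108 of 675 subjects had discontinued by protocol Amendment 1. The rate ratios show direction only.

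Confidence is moderate to high on the text and low on the size. The columns are descriptive (SAP 1.8.3 plans no testing), so this is a labelling fault in the primary-objective tables, not a false inference. Nor would a split make the two doses a randomized comparison, because switching follows physician judgement.

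**What to change.** In SAP 1.2, 1.6, 1.9.1, 1.9.2 and 2.4.1, state one rule for the two pooled dose columns: events and person-time are attributed by the regimen at onset. Each 150-to-300 mg switcher is split at the first 300 mg dose after the switch, whether or not an event occurred. Earlier events and time go to Any 150 mg; later ones go to Any 300 mg, with the clock restarted. Reconcile the Safety set definition, the pooling note, the exposure formula, the AE and laboratory censoring rules and the general rate definition with this rule. If the PDS already contains a split, bring it into the SAP. Make exposure-adjusted rates the main summary in these columns.

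The cost is wording and modest programming; dosage changes are already tracked in the IRT (Protocol 8.3). There are two downsides to state. Switchers appear in both columns, so the columns no longer sum to Any AIN457. Crude percentages will also mix segments of different length, about 2 years after the switch (104 weeks) beside 5 years (260 weeks) for others, which can lower the crude Any 300 mg figure for reasons unrelated to dose. Both need a footnote.

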3.1 Study design

This is a multicenter, double-blind and open label, trial in subjects with moderate to severe chronic plaque-type psoriasis who completed treatment in the maintenance period of studies CAIN457A2304 or CAIN457A2307. It was expected that approximately 740 subjects would be enrolled at approximately 130 study sites worldwide. When recruitment was complete, 675 subjects had been enrolled at 112 sites.

This extension study consists of four periods: the screening period, the treatment period, and two follow-up periods (follow-up and follow up 2). An outline of the visits is presented in Figure 3-1, while a detailed visit schedule can be found in [Table 6-1](#).

Screening Period

The screening period for the extended maintenance portion of the study is the duration between the signing of the informed consent form and enrollment registered with the interactive response technology (IRT). There are no additional requirements for the treatment period other than subjects are required to complete year 1 of the core studies and all assessments at the end of maintenance visit (Week 52) of core study CAIN457A2304 or end of maintenance visit (Week 40) of core study CAIN457A2307. Subjects who complete the EOM visit and assessments of the core studies and consent to the extension will continue directly into the treatment period of this extension study. Subjects must sign the informed consent form (ICF) for the treatment period once the core assessments have been completed for Week 52 of the core studies and the IRT called to register that the subject completed the core study (CAIN457A2304 or CAIN457A2307). For the purpose of reading and understanding, the ICF can be provided to subjects anytime during the core studies, for example, between Week 48 and prior to the dose at Week 52 of study CAIN457A2304 (Weeks 36 and 40 from study CAIN457A2307 are equivalent to Weeks 48 and 52 of CAIN457A2304). However, subjects will NOT sign the ICF before completing the core studies' EOM assessments.

Note: subjects from CAIN457A2307 started their visits in that study after completing 12 Weeks of the CAIN457A2304 core study; therefore, Week 40 of the CAIN457A2307 study is equivalent to Week 52 of the CAIN457A2304 and CAIN457A2304E1 studies as regards previous treatment duration (i.e., 52 weeks).

The dose administered at Week 52 is the first dose of the CAIN457A2304E1 treatment period.

Treatment Period

The treatment period is defined as Weeks 52 through 260.

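### In entire-period safety tables the 300 mg open-label column starts at the first A2304 dose, so it reports 10 mg/kg i.v. time and possible 150 mg induction time as 300 mg

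*SAP*

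**What the plan says.** **Route into the OL group.** SAP Section 1.2 says that Week 12 partial responders "will enter A2307 double blind i.v. period (for 8 weeks) and these subjects will be randomized with 1:1 ratio into either" of two arms, namely 300 mg s.c. or 10 mg/kg i.v. Open-label treatment comes after that: "All the subjects will enter open label 300 mg s.c. secukinumab maintenance period from week 8 to week 40". Protocol Section 3.1 fixes the time axis: "subjects from CAIN457A2307 started their visits in that study after completing 12 Weeks of the CAIN457A2304 core study". Before Week 12 these subjects were in A2304 induction, randomised 1:1 to 150 mg or 300 mg (SAP 1.2).

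**Reporting groups.** SAP 1.2 lists one group for them, AIN457 300 mg OL, and includes it in Any AIN457 300mg and Any AIN457. Table 1-2 plans safety analysis for all three. There is no i.v. group.

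**Periods.** SAP 1.2 defines the entire study and entire treatment periods by components, starting "Combination of Induction (in A2304 core) period + Maintenance (in A2304 and in A2307) period", then core follow-up where relevant and the extension. Each definition ends with a bracketed span that starts at the initial A2304 randomisation.

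**Exposure and events.** SAP 1.6 states that "for entire study period duration of exposure will be defined as the time from first dose of study medication in core study", and it runs until extension treatment ends; its formula subtracts nothing in between. SAP 1.4.1 makes first dose mean the core first dose unless stated otherwise. SAP 1.9 counts core and extension events for the entire treatment period. SAP 1.9.1 treats any event starting after first dose, up to the end limit, as treatment-emergent.

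**Attribution.** SAP 1.9: "Safety analyses will be performed on treatment received or actual treatment", with a cross-reference to Section 1.2. There, treatment received equals treatment randomised unless the wrong treatment was given throughout the study.

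**The concern.** Together these rules make the OL column cover up to 20 weeks before open-label 300 mg s.c. began. Some of that time was on 10 mg/kg i.v., and some may have been on 150 mg s.c. All of it carries a 300 mg label and feeds the pooled 300 mg column.

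Crude incidence and exposure-adjusted incidence both use a subject's first event, so early time weighs more than its share of the calendar. A subject whose first event falls on i.v. also stops contributing time at risk for that event during the later years on 300 mg s.c.

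The component list and the bracket also name different weeks, so two programmers could build different tables from one definition. Safety and tolerability is the primary objective, and these are core outputs for it.

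**Working it through.** **1. Locate the weeks.** A2307 Week 0 is A2304 Week 12, and A2307 Week 40 is Week 52 (12 + 40 = 52). The double-blind period is therefore Weeks 12-20, 8 × 7 = 56 days, and open-label 300 mg s.c. starts at Week 20.

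**2. Compare list and bracket.** The list names A2304 induction, then maintenance in A2304 and A2307. A2307 maintenance is A2307 Weeks 8-40, so Weeks 12-20 are in no listed component. The bracket, the SAP 1.6 formula, and the event rules in SAP 1.9 and 1.9.1 all include them.

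**3. Look for a rule that separates the time.** The treatment-received rule works per subject and changes only if the wrong treatment was given throughout. The censoring at switch date in SAP 1.9.1 does not help, because OL subjects have no Week 156 switch. None was found.

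**4. Group size.** The SAP states no figure, so use Protocol Section 9.7. Eligible: 918 × 0.95 × 0.85 = 741 (stated about 740). Per A2304 group: 741.3 × 0.80 / 4 = 148.3 (stated 148). Left for OL: 740 − 4 × 148 = 148. This is a ceiling, because Week 12 non-responders were discontinued. At a 1:1 ratio about 74 would have had i.v.

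**5. Person-time on i.v., full follow-up to Week 260 assumed.**
- Per i.v. subject: 56 / 1,820 = 3.1%.
- Column at the ceiling: 74 × 56 / 365.25 = 11.3 patient-years, out of 148 × 1,821 / 365.25 = 737.9, or 1.5%. The percentage does not depend on the group size.
- Pooled 300 mg, taking three groups of 148: 11.3 / 2,213.6 = 0.5%. Subjects who switch from 150 mg would lower this further.

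**6. First events on i.v.** Assume a constant rate r per year, equal on both routes, and follow-up to Week 260. The share of first events by week w is S(w) = (1 − exp(−r·w/52.18)) / (1 − exp(−r·260/52.18)). Weeks 12-20 hold S(20) − S(12), and half of that is i.v.

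| Rate per 100 patient-years | Weeks 12-20 | i.v. half |
|---|---|---|
| 10 | 3.8% | 1.9% |
| 30 | 5.4% | 2.7% |
| 60 | 8.1% | 4.0% |
| 100 | 11.4% | 5.7% |
| 200 | 16.7% | 8.3% |

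At 0.5 to 2 per 100 patient-years the i.v. half is about 1.6%.

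**7. 150 mg induction.** For a subject induced on 150 mg, 84 / 1,820 = 4.6% of the time is mislabelled. The share of OL subjects so induced is not given. At an assumed 50% to 80% it is 2.3% to 3.7% of column person-time. S(12) is 5.8% at 10 and 36.9% at 200 per 100 patient-years, so at an assumed 50% the mislabelled first events would be 2.9% to 18.4%.

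**The case against.** **Treatment received.** A reader might infer that the plan breaches its own treatment-received requirement. It does not clearly do so: SAP 1.9 points to Section 1.2, where the term is a subject-level assignment to the randomised treatment. The fair criticism is that this rule cannot describe subjects whose dose and route changed between periods.

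**Lost events.** A reader might infer from the component list that i.v.-period events are dropped while their exposure stays in the denominator. Only a literal reading of the list supports that. The bracket, SAP 1.4.1, 1.9 and 1.9.1 all bring those events in, so mislabelling is the better-supported outcome.

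**Objective.** The primary objective is long-term safety and tolerability of secukinumab, not safety by dose and regimen, and no formal testing is planned. That lowers the stakes but does not make the label correct.

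**Size.** The share of first events in Weeks 0-20 (9.6% to 53.5% over the same rates) might be read as the i.v. effect. It is not: Weeks 0-12 were s.c. induction, and half the subjects in Weeks 12-20 were assigned 300 mg s.c. At 90 kg, the core stratification cut, 10 mg/kg is 900 mg. That is per administration, and the dosing frequency in that period is not given, so it does not measure cumulative exposure.

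**Outputs.** SAP 1.9.1 ties exposure-adjusted adverse event rates to yearly intervals in the fixed-interval cohorts, so it is unclear whether they are produced for OL alone. The whole-period crude incidence (1.9.1), the neutropenia rate (1.9.2) and notable vital signs (1.9.3) remain exposed.

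**Conclusion.** The point holds. Followed as written, the plan reports A2307 i.v. time, and any 150 mg induction time, as 300 mg in the OL and pooled 300 mg columns of the entire-period safety tables. The period definition in SAP 1.2 is also inconsistent with itself.

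The i.v. effect is modest: about 1.5% of OL person-time, about 0.5% of a three-group pooled column, and about 1.9% to 8.3% of OL first events at 10 to 200 per 100 patient-years. These figures rest on the 1:1 randomisation ratio carrying over to extension entrants, full follow-up, and a constant rate equal on both routes. The actual OL group size, i.v. share and induction-dose split are not given, so the induction part can only be shown as a range. The i.v. share of time is larger for subjects who leave early: 56 / 364 = 15.4% for an i.v. subject followed only to Week 52. A single rare serious event on i.v. would also appear as a 300 mg event.

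Extension-only tables and the yearly fixed-interval tables are unaffected.

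**What to change.** In SAP 1.2, 1.6 and 1.9:
- Add the A2307 double-blind period to the component lists of both entire-period definitions, so that list and bracket name the same weeks for events and for exposure.
- In entire-period tables, attribute OL subjects' events and exposure by dose received. Put 10 mg/kg i.v. time in its own column and in Any AIN457 only. Keep 150 mg induction time out of the 300 mg columns. Retain 300 mg s.c. time, including the A2307 s.c. arm, in Any AIN457 300mg.
- State the start date of the 300 mg OL column.
- State which column takes an event that begins after i.v. dosing but within the 84-day window. Moving the start date alone does not settle this.

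**Cost.** SAP wording and some extra programming, using dosing dates already held in the core databases. The OL and pooled 300 mg columns lose a little person-time, and the OL column would start later than the fixed-interval and start-of-relapse columns, which needs a footnote.
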